4.7.1.1. Adverse Events and Serious Adverse Events

Adverse events (including serious adverse events (SAE), AEs causing permanent treatment discontinuation, deaths, and AEs of special interest) are recorded from the time of signed

informed consent until the end of study. All AEs diagnosed by the Investigator will be reported and described.

All AEs will be dictionary coded by "lowest level term (LLT)", "preferred term (PT)", "high level term (HLT)", "high level group term (HLGT)" and associated primary "system organ class (SOC)" using the version of MedDRA in effect at the time of database lock for the analysis.

Adverse Event Observation Period

- Pre-treatment AEs are AEs that developed or worsened or became serious during the pre-treatment period.
- Treatment-emergent adverse events (TEAEs) are AEs that developed or worsened or became serious during the TEAE period.
- Post-treatment AEs are AEs that developed or worsened or became serious during the post-treatment period.

4.7.1.2. Adverse Events of Special Interest

Adverse events of special interest (AESI) are AEs (serious or non-serious) required to be monitored, documented, and managed in a pre-specified manner as described in the protocol.

In this study, AESI are the following (their complete descriptions are provided in the protocol):

- Local injection site reactions, selected using an e-CRF specific tick box on the AE page;
- General allergic events will be tabulated. Events will be selected using standardized MedDRA query (SMQ) "hypersensitivity" (broad and narrow) excluding the preferred terms linked to local injection site reactions (i.e. preferred terms containing "injection site" or "infusion site")
- ALT ≥3 ULN in the case baseline ALT < ULN or ALT ≥2 times the baseline value in the case baseline ALT ≥ ULN, selected using laboratory data. Baseline to be considered is the baseline of the present OLE study.
- Neurologic events selected using SMQs "demyelination" (broad and narrow), "peripheral neuropathy" (broad and narrow), and "Guillain-Barre syndrome" (broad and narrow) excluding the following preferred terms: "acute respiratory distress syndrome", "asthenia", "respiratory arrest" and "respiratory failure" and including selected PTs from SMQ "optic nerve disorders" (see Appendix 10.3, Table 3 for the list of terms)

- Symptomatic overdose with investigational medicine product, selected using HLT "Overdose" and the tick box "Symptomatic Overdose" in the e-CRF AE page.
- Pregnancy of female patient/subject (including male subject's partner), selected using appropriate MedDRA codes (PT "Pregnancy").
- Neurocognitive events:
 - Selected using a company MedDRA query (CMQ), based on the following 5 HLGTs: "deliria (including confusion)", "cognitive and attention disorders and disturbances", "dementia and amnestic conditions", "disturbances in thinking and perception", and "mental impairment disorders".
 - A second grouping of terms for neurocognitive events was defined based on Regulatory Agency request (FDA CMQ) (see Appendix 10.3, Table 4 for the list of terms)
- Cataract using HLT "Cataract conditions"
- New onset of diabetes (NOD) will be assessed in patients without diabetes at baseline (defined as patients without diabetes at baseline and during the study in the neurocognitive function study (R727-CL-1532)): The definition of new onset of diabetes (NOD) will be the following:
 - Type 1 or type 2 diabetes TEAE (grouping of Medical Dictionary for Regulatory Activities [MedDRA®] terms in Appendix 10.7 Table 7)

and/or

- At least 2 values of HbA1c \geq 6.5% during the TEAE period

NOTE: For patients with only a single measurement available during the TEAE period, a single value $\geq 6.5\%$ will be considered and qualify the patient as NOD by default.

For patients with several HbA1c measurements but only with the last one $\geq 6.5\%$, this single value $\geq 6.5\%$ will be considered and qualify the patient as NOD by default

and/or

- At least 2 values of fasting plasma glucose (FPG) \geq 126 mg/dL (7.0 mmol/L)

NOTE: For patients with only a single measurement available during the TEAE period, a single value $\geq 126 \text{ mg/dL}$ (7.0 mmol/L) will NOT be considered and will NOT qualify the patient as NOD

For patients with several FPG measurements but only with the last one ≥ 126 mg/dL (7.0 mmol/L), this single value ≥ 126 mg/dL (7.0 mmol/L) will NOT be considered and will NOT qualify the patient as NOD

Analyses of NOD events will also be provided using the tick box on the e-CRF AE page as a second approach.

In addition, the following grouping of events will be provided:

- Hepatic disorder events using SMQ "Hepatic disorder"
- Diabetes mellitus or diabetic complications using 1/ the HLGT "diabetes complications" (including PTs pertaining to the secondary SOC included in the HLGT),2/ the HLT "diabetes mellitus", 3/ the HLT "carbohydrate tolerance analyses (incl diabetes)" excluding PTs "blood glucose decreased" and "Glycosylated haemoglobin decreased" and 4/ from the HLT "Hyperglyceamic conditions NEC" only the following PTs "hyperglycaemia", "Hyperglycaemic unconsciousness" and "Hyperglycaemic seizure"

Neurocognitive Events of Special Interest

Neurocognitive events are defined in this study as AESI, specifically, neurocognitive AEs (serious or nonserious) required to be monitored, documented, and managed in a prespecified manner as described in this protocol. The neurocognitive events will be adjudicated by the neurocognitive events review committee which is composed of experts in the field of cognition, independent from the sponsor and the investigators. This committee will be responsible for defining, validating, and classifying AEs of interest possibly related to cognition impairment. A charter and an operational manual will specify the procedures and criteria used for review of these events.

The committee will adjudicate whether a neurocognitive event identified by investigator or the CMQs is indeed a neurocognitive event (Yes/No).

The committee will also adjudicate whether possible etiology of the neurocognitive event is identified.

- Yes: means that there is a clear alternative explanation for the neurocognitive event.
- No: means that there is no clear alternative explanation for the neurocognitive event, and it might be study related.

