### 9.4.3. Other Events that Require Accelerated Reporting to Sponsor

The following events also require reporting to the sponsor (or designee) within 24 hours of learning of the event:

**Symptomatic Overdose of Study Drug:** Accidental or intentional overdose of at least 2 times the intended dose of study drug within the intended therapeutic window, if associated with an AE,

**Pregnancy:** Although pregnancy is not considered an AE, it is the responsibility of the investigator to report to the sponsor (or designee), within 24 hours of identification, any pregnancy occurring in a female or female partner of a male, during the study or within 180 days of the last dose of study drug. Any complication of pregnancy affecting a female study patient or female partner of a male study patient, and/or fetus and/or newborn that meets the SAE criteria must be reported as an SAE. Outcome for all pregnancies should be reported to the sponsor.

Adverse Events of Special Interest: All AESI, serious and nonserious, must be reported within 24 hours of identification using the same reporting process as for SAE reporting, per Section 9.4.2. Adverse events of special interest for this study include the following:

- ALT ≥3 upper limit of normal (ULN; if baseline ALT < ULN) or ALT ≥2 times the baseline value (if baseline ALT ≥ ULN). Baseline to be considered is the baseline of the present OLE study.
- Allergic events and/or local injection site reactions that are allergic in nature and that require consultation with another physician for further evaluation
- Neurologic events that require additional examinations/procedures and/or referral to a specialist
- All neurocognitive events
  - Neurocognitive AEs will be reviewed on a regular basis by an independent panel of experts (neurologists/specialists of neurocognition) to ensure that all the necessary information pertinent to these AESIs is collected
- Cataracts
- New onset of diabetes

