- All grouping of TEAEs including adverse events of special interest, as listed in Section 4.7.1.2, will be presented by SMQ/CMQ and PT (when selection is based on SMQs/CMQs) and by SOC and PT (when selection is based on the e-CRF tick box or HLGT/HLT). The summaries will be sorted by decreasing incidence of PT within each SOC/SMQ (in the PRALUENT group).
- Neurocognitive events adjudicated by the neurocognitive events review committee will also be summarized by primary SOC and PT. They will also be summarized according to the adjudication of possible etiology of the neurocognitive events (Yes/No) (Section 4.7.1.2).
- All TEAEs within diabetes grouping will be analyzed overall and according to the diabetic status at baseline.
The following variables will also be tabulated for the local injection site reactions TEAEs:

- Intensity of the event (mild, moderate, severe);
- Number of events divided by the number of study treatment injections received;
- Time from first study treatment injection to first injection site reaction;
- Description of the highest intensity of each symptom recorded in the specific e-CRF page with table and bar chart.

Description of symptoms and possible etiologies for General Allergic Reaction TEAE reported by investigator (using the tick box), will be presented.

Post-treatment adverse events

- All post-treatment AEs by primary SOC and PT, sorted by the internationally agreed SOC order and decreasing incidence of PTs (in the PRALUENT group) within each SOC;
- All post-treatment SAEs by primary SOC and PT, sorted by the sorting order defined above.

Subgroup of patients with two consecutive LDL-C <25 mg/dL (<0.65 mmol/L)

If applicable, similar summaries of TEAEs as those described above will be provided on the safety subgroup population of patients with two consecutive results of LDL-C <25 mg/dL (as defined in Section 4.8) in both patient groups. Only TEAEs for which it will be confirmed or unclear that they occurred, worsened or became serious on the day or after the day the first level of LDL-C <25 mg/dL was observed will be considered in this summary.

In addition, the neurocognitive event rate in patients with 2 consecutive results separated by at least 21 days for calculated LDL-C <25 mg/dL, and calculated LDL-C <15 mg/dL, will be assessed.

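### Injection site reactions enter the local AESI by tick box but leave the allergic AESI by preferred-term wording, so events on which box and term disagree can fall in neither group or in both

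*SAP*

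**What the plan says.** SAP section 4.7.1.2 defines the two groups separately.

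- The local group is "Local injection site reactions, selected using an e-CRF specific tick box on the AE page". No preferred-term rule is given for it.
- The general allergic group is the hypersensitivity SMQ, broad and narrow, "excluding the preferred terms linked to local injection site reactions". The SAP identifies those terms by wording alone, namely *injection site* or *infusion site*. The tick box plays no part in the removal.

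SAP section 5.7.1 tabulates each grouping according to how it was selected: "by SMQ/CMQ and PT (when selection is based on SMQs/CMQs) and by SOC and PT (when selection is based on the e-CRF tick box" and related term levels. For local reactions it adds, among other summaries, "Number of events divided by the number of study treatment injections received" and the time from first injection to first reaction.

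Protocol section 9.4.3 treats the two as one AESI: "Allergic events and/or local injection site reactions that are allergic in nature and that require consultation with another physician for further evaluation". AESIs are one of the event types named under the primary endpoint (protocol section 4.2.1, SAP section 4.6.1).

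**The concern.** The exclusion is justified by the terms being linked to local reactions, so it presumes that the excluded events are counted in the local group. Nothing puts them there unless the site ticked the box. In the other direction, ticking the box does not take an event out of the general allergic group if its coded term lacks the site wording.

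At stake is the content of two AESI tables that describe part of the primary endpoint. The protocol's allergic AESI expressly includes injection site reactions of an allergic kind, and these are the events that can miss both tables. The events-per-injection figure and the time to first reaction inherit any omission from the local set.

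**Working it through.** No arithmetic applies and the plan gives no figure to reproduce. The check is to apply the two SAP rules to an event whose preferred term lies in the hypersensitivity SMQ.

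| Tick box | Term has site wording | Local AESI | General allergic AESI | Result |
|---|---|---|---|---|
| Yes | Yes | in | removed | local only |
| Yes | No | in | in | both |
| No | Yes | out | removed | neither |
| No | No | out | in | allergic only |

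The first and last rows behave as a local/general split should. The middle two do not. The *neither* row needs the coded term to carry the excluded wording; an unticked site event coded without it stays in the allergic group. For a site-worded term outside the SMQ, an unticked event is missing from the local table but was never a candidate for the allergic one.

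Next, does anything elsewhere reconcile the two rules?

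- **SAP 5.7.1, allergic tick box.** A general allergic reaction tick box is used, but only to describe symptoms and possible causes. It does not select the AESI.
- **SAP 5.7.1, grouping tables.** Each grouping is reported by its own selection rule. No cross-check or precedence is stated.
- **SAP 5.7.1, all treatment-emergent events.** Tables by SOC and PT include every such event, so one in the *neither* row remains visible there under its own term.
- **Protocol 11.1.** Data validation and coding are left to a data management plan and a medical coding plan. No check of box against term is stated.
- **SAP 4.7.1.2, other AESIs.** New-onset diabetes is defined by terms and laboratory values, with the tick box as a second approach. Neurocognitive events go to adjudication if either the investigator or the company MedDRA queries identify them. The SAP thus uses two sources for these AESIs but only one for injection site reactions.

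The gap therefore follows from the text. How often it is met does not: the documents give no miss rate for the tick box, no incidence of site-worded terms and no coding convention for local reactions.

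**The case against.** The strongest reply is that little is lost and the problem belongs to data cleaning.

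- **Site-worded events are meant to be outside a group called general allergic events.** This stands. An unticked event of this kind is missing from the local table; it is not wrongly missing from the allergic one, and the remedy returns it only to the local group. A reader might infer that the allergic count should regain these events, but the SAP's deliberate exclusion does not support that.
- **The events do not vanish.** This stands. They remain in the all-event tables. It does not repair the AESI tables or the per-injection summaries.
- **The protocol's allergic events are unlikely to go unflagged.** Protocol 9.4.3 requires them to be reported within 24 hours, and 9.5.1 asks for local reactions to be reported in detail. This makes a missed box less likely for the referred cases, but neither section makes the box part of the process.
- **Checks may exist in plans that are not public.** Possibly so. A selection rule for an AESI should nevertheless be complete in the SAP.
- **Overlap does no harm.** Groupings are tabulated separately, no summed AESI total is planned, and the SAP accepts overlap elsewhere. A reader might infer that local reactions inflate the allergic group. That requires ticked reactions to be coded to SMQ terms without site wording, which the documents neither show nor rule out.
- **Simply adding all site-worded terms would bring in error.** This stands. Study drug is given only by subcutaneous auto-injector, and other concomitant medications are allowed. Infusion site terms, or reactions to other injected products, would enter the numerator of a rate whose denominator is study injections. The remedy has to be limited accordingly.
- **The study is single-arm, ended early and descriptive.** True, and no test is affected. Description of AESIs is nevertheless part of what the study sets out to report.

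**Conclusion.** The point holds as a classification gap. SAP 4.7.1.2 uses one variable to admit events to the local group and another to remove them from the allergic group, and neither document reconciles them. Where box and term disagree, SMQ events go to neither AESI table or to both.

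The size is unknown. A reader might try to put a number on it. With the protocol's expected 1600 patients, an assumed 5% with any injection-site term gives 1600 × 0.05 = 80; an assumed miss rate of 5% to 20% then gives 80 × 0.05 = 4 to 80 × 0.20 = 16 patients. The documents do not support that as an estimate. Both rates are assumptions, 1600 is anticipated enrolment, the base covers all site terms and not only allergic ones, and a patient with another ticked reaction would still be counted. At most it illustrates possible omissions from the local table.

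The conclusion rests on the written rules alone and on no assumed rate. The likely effect is modest, but it falls on a named part of the primary endpoint and is cheap to remove.

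**What to change.** In SAP 4.7.1.2:

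1. Keep the tick-box selection of local injection site reactions, and add a second approach, as is done for new-onset diabetes. Under it, an event is local if the box is ticked **or** its preferred term contains *injection site*, limited to reactions at a study-drug injection site.
2. Exclude from general allergic events every event selected as local under that rule, together with the site-worded terms already excluded.

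In SAP 5.7.1, run the per-injection rate and the time to first reaction on both sets.

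Before database lock, list every event on which box and term disagree, and query it with the site.

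Under these rules a ticked event is local only, and an unticked injection-site event is local once attributed to study drug. Unticked events with infusion site wording, or attributed to another product, stay outside both groups by design and remain in the all-event tables.

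The cost is a few lines of SAP wording, one selection flag, one listing and a second run of two summaries. Unticked events will lack the dedicated symptom page, so they can be counted but not described by symptom, and their attribution to a study-drug injection must be checked individually.

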4.6.1. Primary Endpoint

The primary endpoint in the study is the incidence of AEs after first administration of study drug through the last dose of study drug plus 2 weeks.

The following AEs will be described:

- AEs/serious adverse events (SAEs)
- AEs leading to treatment discontinuation
- Adverse events of special interest (AESI)

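### Two of the protocol's six AESI categories (allergic/injection-site and neurologic) are tabulated in the SAP without their qualifying conditions, and pregnancy and symptomatic overdose are labelled AESI, with no declared change

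*SAP*

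**What the plan says.** Both documents name AESI among the three event types to be described under the primary endpoint (Protocol 4.2.1; SAP 4.6.1, "Adverse events of special interest (AESI").

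Protocol 9.4.3 lists six AESI categories. Two carry a qualifying condition:

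- The allergic category is worded "Allergic events and/or local injection site reactions that are allergic in nature and that require consultation with another physician for further evaluation".
- The category for the nervous system is worded "Neurologic events that require additional examinations/procedures and/or referral to a specialist".

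The other four are an ALT rule, all neurocognitive events, cataracts and new-onset diabetes. Symptomatic overdose and pregnancy are separate entries in the same section, outside the AESI list. Of the latter the protocol says: "Although pregnancy is not considered an AE".

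SAP 4.7.1.2 gives these rules instead:

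- Injection site: "Local injection site reactions, selected using an e-CRF specific tick box on the AE page".
- Allergic: the hypersensitivity SMQ, broad and narrow, less injection-site and infusion-site terms.
- Neurologic: "Neurologic events selected using SMQs 'demyelination' (broad and narrow), 'peripheral neuropathy' (broad and narrow", then the Guillain-Barre SMQ, less four preferred terms, plus selected optic-nerve terms.
- Symptomatic overdose and pregnancy appear in the list as AESI.

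SAP 5.7.1 builds the AESI tables from the list in 4.7.1.2. SAP 1.2.3, on modifications from the protocol's statistical section, mentions only that early termination makes all analyses descriptive.

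**The concern.** The protocol asks, for these two categories, what the event led to. The SAP asks how the event was coded or whether a box was ticked. A neurologic event that a site judged to need referral, and so had to report within 24 hours, is absent from the neurologic AESI table if its term lies outside the chosen queries. An event with a listed term enters that table even if nobody investigated it. Allergic and injection-site tables include events that needed no consultation.

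This is an uncontrolled descriptive safety study, so the counts are the result. A reader comparing the report with the protocol would take the AESI tables as showing the protocol's AESI, and they would not reconcile with what sites reported under that name. Any Kaplan-Meier display of a neurologic or allergic AESI, which SAP 5.7.1 allows, would inherit the same definition.

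**Working it through.** No formula applies. The plan states no sample size (SAP 2.2) and plans no formal test (SAP 5), so there is no figure to reproduce. The check sets the two lists side by side.

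| Item | Protocol 9.4.3 | SAP 4.7.1.2 | Result |
|---|---|---|---|
| ALT | AESI, numeric rule | same rule, applied to laboratory data | carried over |
| Neurocognitive | AESI, all events | two term lists; investigator- or list-identified events adjudicated | kept, made operational |
| Cataract | AESI | one HLT | kept, made operational |
| New-onset diabetes | AESI | terms, HbA1c or glucose; tick box as second approach | kept, made operational |
| Allergic / injection site | AESI if consultation needed; site reactions must be allergic | two groupings, neither condition applied | redefined |
| Neurologic | AESI if tests or referral needed | three SMQs plus optic terms, no condition | redefined |
| Symptomatic overdose | separate item | AESI | added to label |
| Pregnancy | separate item, not an AE | AESI | added to label |

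Of the six protocol categories, four are kept and two are redefined. Two items are added to the label.

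**Neurologic set.** Let P be neurologic events that needed tests or referral, whatever their term. Let S be events with a term in the SAP grouping, whatever was done about them.

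- In P but not S: any referred event coded outside the three SMQs and the optic list. The protocol sets no limit on terms, so such events are possible. SMQ contents are not in the documents, so no specific term is asserted here.
- In S but not P: any listed term without work-up. Appendix 10.3 Table 2 includes reduced visual acuity and night blindness, for example.

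Hence S is neither a subset nor a superset of P. A total for S could lie above or below the total for P.

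**Allergic and injection-site set.** The tick box takes in non-allergic reactions and reactions without consultation. If sites tick it for every local reaction, the SAP count is at or above the protocol count. The hypersensitivity grouping likewise includes events without consultation. Whether it also captures every protocol event cannot be checked without the SMQ contents.

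**Is there text that bridges the gap?** SAP 4.7.1.2 refers to the protocol for full descriptions, but SAP 5.7.1 tabulates from the SAP's own list. The investigator's tick box for general allergic reactions is used in 5.7.1 only to describe symptoms and possible causes. No investigator-identified output is named for neurologic events. By contrast, diabetes has one, and for neurocognitive events "The committee will adjudicate whether a neurocognitive event identified by investigator or the CMQs is indeed a neurocognitive event (Yes/No".

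**Table references in SAP 4.7.1.2.**

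| Term list | SAP cites | Actual place |
|---|---|---|
| Optic terms | Appendix 10.3 Table 3 | Appendix 10.3 Table 2 |
| FDA neurocognitive list | Appendix 10.3 Table 4 | Appendix 10.3 Table 3 |
| Diabetes terms | Appendix 10.7 Table 7 | Appendix 10.3 Table 4 |

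Read literally, the first reference puts the neurocognitive list into the neurologic grouping and the second makes the diabetes list the neurocognitive one. The third points to an appendix that does not exist.

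**The case against.** The strongest reply is Protocol 10.4.4.1, which foresees treatment-emergent AESI defined by a preferred term or a prespecified grouping. Selecting by SMQ is therefore what the protocol announced. The conditions in 9.4.3 can also be read mainly as instructions to sites on what to report quickly. Standard queries are reproducible, whereas referral habits vary by site. This stands as far as it goes: using queries is not a departure, and the groupings deserve to stay. It does not explain why no output identifies the events that met the protocol's own conditions, or why the difference is undeclared.

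A second reply is that nothing disappears. All TEAEs are tabulated by SOC, HLGT, HLT and PT, and serious ones are listed as well (SAP 5.7.1). That is correct. A referred neurologic event outside the queries is reported there, though not marked as an AESI.

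Third, the table-reference errors are editorial, since the lists in Appendix 10.3 carry titles that show their content. That is fair, but a programmer who follows the numbers would build the wrong groupings.

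**Conclusion.** The mismatch holds for two of six protocol categories, together with two items labelled AESI that the protocol lists elsewhere, none of it declared in SAP 1.2.3. The effect is on descriptive AESI counts only; no test, error rate or sample size depends on it. How many patients are affected cannot be worked out, because the documents give neither event rates nor SMQ contents.

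Three stronger readings are tempting, and the documents do not support them:

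- A reader might infer that the AESI part of the primary endpoint as a whole is not measured as defined. Four categories are kept, groupings are permitted, and the omitted events remain in the all-TEAE tables.
- A reader might infer that pregnancy and overdose inflate an AESI incidence. SAP 5.7.1 plans no pooled AESI figure: the TEAE overview has no AESI row, and AESI are shown by grouping. The fault is one of labelling.
- A reader might infer that investigator reports should replace the SAP's rules throughout. That would be worse for ALT, where the SAP already applies the protocol's rule to laboratory values, and for neurocognitive events, where it takes investigator-identified and list-identified events and has them adjudicated.

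The conclusion assumes that SAP 4.7.1.2 will be programmed as written and that no separate specification restores the protocol's conditions.

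**What to change.** Keep the SMQ and CMQ groupings, and leave the ALT, neurocognitive, cataract and diabetes rules as they are. Then:

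1. In SAP 5.7.1, add a tabulation of (a) neurologic events and (b) allergic events and allergic injection-site reactions that the investigator reported as AESI under Protocol 9.4.3, labelled as a second approach in the way already done for new-onset diabetes. Use the allergic tick box together with the AESI reports in the AE eCRF or safety database. A neurologic AESI flag is assumed; if there is none, use the 24-hour reports, which Protocol 9.4.3 routes through the SAE process of 9.4.2.
2. Label pregnancy and symptomatic overdose as separate accelerated-report items.
3. State in SAP 1.2.3 the differences from Protocol 9.4.3 that remain.
4. In SAP 4.7.1.2, point the optic terms to Appendix 10.3 Table 2, the FDA neurocognitive list to Appendix 10.3 Table 3, and the diabetes terms to Appendix 10.3 Table 4.

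The cost is SAP wording and one or two extra tables. The study has already been terminated, so the added tables depend on what sites recorded. Protocol 9.4.3 required these reports, but the CRF itself is not among the documents.

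### New-onset diabetes can rest on one unconfirmed HbA1c of 6.5% or more when it is the only or last value, and the planned tables do not show how many cases do

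*SAP*

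**What the plan says.** SAP 4.7.1.2 lists NOD among the adverse events of special interest (AESI). The at-risk group is patients without diabetes, "defined as patients without diabetes at baseline and during the study in the neurocognitive function study"; no HbA1c ceiling is stated. A patient is a case through any of three routes: a diabetes TEAE, an HbA1c criterion or a fasting plasma glucose (FPG) criterion.

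The main HbA1c criterion is "At least 2 values of HbA1c" at or above 6.5% in the TEAE period. The values need not be consecutive, and no rise from baseline is required. Two notes relax it:

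- Only value: "For patients with only a single measurement available during the TEAE period, a single value" of 6.5% or more counts.
- Last value: "For patients with several HbA1c measurements but only with the last one" at or above 6.5%, that one value counts.

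In both situations the value "will be considered and qualify the patient as NOD by default". For FPG at 126 mg/dL the notes cover the same two situations and decide the other way: the value "will NOT be considered and will NOT qualify the patient as NOD". No reason is given for the difference.

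The section adds a parallel analysis: "Analyses of NOD events will also be provided using the tick box on the e-CRF AE page as a second approach". SAP 5.8 summarises HbA1c by visit, also by baseline diabetes status, and plots it over time. SAP 1.1 records early termination by the sponsor on 31 January 2020. SAP 2.1 describes the study as uncontrolled, and SAP 5 makes all analysis descriptive.

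**The concern.** A patient whose true HbA1c is stable at 6.3% or 6.4% can be in the at-risk group, 0.1 to 0.2 points below the case line. Under the two notes, any patient whose final HbA1c is 6.5% or more is a case, whatever came before. The series 6.4, 6.4, 6.5 is a case; 6.5, 6.4, 6.4 is not. Which value is last can be fixed by a visit schedule, a withdrawal or, here, the sponsor's decision to stop.

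The summary groups in SAP 5 are the former parent-study arms, and all of these patients now receive PRALUENT. A noise-driven case therefore has no untreated comparison, and the descriptive count is itself the result. At stake is whether a reader of the AESI table takes an unrepeated laboratory value for established new diabetes on drug.

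**Working it through.** **Plan's own figure.** None. The documents give no expected NOD rate and no HbA1c mean or SD, so nothing can be reproduced and the size must rest on assumptions.

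**Inputs from the documents**

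- Case threshold 6.5%, and the two-value rule with its two waivers (SAP 4.7.1.2).
- HbA1c belongs to blood chemistry (Protocol 8.2.2.3). Table 1 schedules chemistry at weeks 24, 48, 72, 96, 120, 144, 168 and 192, so there are at most 8 scheduled post-baseline values.

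**Assumptions**

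- True HbA1c is constant in each patient (no drug effect), Normal with mean 5.8% and between-patient SD 0.35, cut below 6.5%.
- Within-patient SD is 0.20, with independent errors.
- Results are reported to 0.1, so a reported 6.5% means a measured 6.45% or more.
- Observed baseline is below 6.5%.

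**Formulas.** For true level μ, within-patient SD σ and k values, let p = P(Z ≥ (6.45 − μ)/σ). Then:

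- two-value rule: 1 − (1 − p)^k − k·p·(1 − p)^(k−1)
- waiver only (the sole high value is the only or last one): p·(1 − p)^(k−1)
- SAP rule: the sum of the two.

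**One patient.** Take μ = 6.3, σ = 0.2 and, for simple numbers, no rounding. Then p = P(Z ≥ (6.5 − 6.3)/0.2) = P(Z ≥ 1) = 0.159.

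- k = 1: the waiver gives 0.159 and the two-value rule 0.
- k = 2: the waiver gives 0.159 × 0.841 = 0.133, the two-value rule 0.159² = 0.025, total 0.159.
- k = 8: the waiver gives 0.159 × 0.841^7 = 0.047, the two-value rule 0.370, total about 0.418.

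**Cohort.** Averaging over the assumed distribution gives the percentage of at-risk patients called NOD with no drug effect:

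| HbA1c values | SAP rule | Two-value rule | Waiver alone | Waiver's share |
|---|---|---|---|---|
| 1 | 2.7 | 0 | 2.7 | 100% |
| 2 | 2.7 | 0.65 | 2.1 | about 76% |
| 4 | 3.7 | 2.35 | 1.4 | 37% |
| 8 | 6.1 | 5.3 | 0.8 | 13% |

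**Range for the waiver alone** (1, 2, 4, 8 values; between-patient SD kept at 0.35):

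- mean 5.7%, σ = 0.10: 0.6, 0.45, 0.3, 0.2 points
- mean 5.8%, σ = 0.25: 3.9, 3.0, 2.0, 1.2 points.

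So the waiver adds about 0.2 to 3.9 points. On the base assumptions but without rounding (6.5 in place of 6.45 in the formula), it adds 2.0, 1.6, 1.1 and 0.7.

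**Parent-study exclusion.** The table conditions on one baseline value only. Without the cut on true HbA1c, the one-value rate is 3.1%. If three parent-study values also had to be below 6.5%, it falls to 1.5%; if the parent study applied this same NOD rule, to 2.1%. Both are assumptions, because the documents do not state how diabetes during the parent study was identified.

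**The case against.** **Counting is the prudent direction in a safety study.** A high last value has been neither confirmed nor refuted, whereas in 6.5, 6.4, 6.4 the later values speak against the first. The SAP leans the same way elsewhere: adverse events with incomplete onset dates are classed as treatment-emergent unless the information shows otherwise (5.7.1), and missing causality is treated as related (6.3). This stands as a reason to keep these patients in the overall count. It does not explain the opposite FPG rule, and it is no reason to leave unconfirmed cases unlabelled.

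**Mitigations exist.** The tick-box analysis gives a second count, and the HbA1c-by-visit summaries could show many NOD cases beside a flat mean. This stands in part. Neither shows how many main-definition cases rest on one value.

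**Stronger readings that a reader might infer, and that do not hold:**

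- *That the waiver produces a very high false rate.* With 8 values and observed baseline 6.0 to 6.4%, the whole HbA1c rule gives nearly 18% on the base assumptions, but the waiver supplies only about 2 points of it. The rest comes from the ordinary two-value rule.
- *That early termination inflates NOD.* Fewer values lower the no-effect total (6.1% with 8 values, 2.7% with 1). What rises is the share resting on one value. The documents do not say how many values patients have.
- *That every such value enters the primary endpoint as an adverse event.* AESIs are described under that endpoint, but a laboratory value is an AE only under the criteria of Protocol 9.4.5. A lone HbA1c of 6.5% enters the NOD tabulation without necessarily being a TEAE.
- *That inference is compromised.* Nothing is tested, so no error rate is at issue.

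**Conclusion.** The point holds as a matter of presentation and interpretability. That unconfirmed HbA1c values count, that FPG is handled the opposite way and that case status depends on when follow-up stops all follow from the text and need no assumption.

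The size does need assumptions. On the base case the waiver adds roughly 27, 21, 14 and 8 no-effect cases per 1,000 at-risk patients with 1, 2, 4 and 8 values. It matters most where follow-up is short, since there it supplies most or all of the no-effect HbA1c cases. The mean, both SDs and the truncation of true HbA1c are assumed, and the parent-study exclusion could bring the figures down by an unknown amount. The documents do not support calling the NOD definition invalid. They support asking that its unconfirmed part be visible. This is a cheap improvement, not a defect that undermines the analysis.

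**What to change.** In SAP 4.7.1.2 and the AESI table, keep the overall NOD count and the diabetes-TEAE route as they are. Split the HbA1c-based cases into two rows:

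- **Confirmed:** at least two values of 6.5% or more in the TEAE period.
- **Unconfirmed:** only or last value 6.5% or more, with no diabetes TEAE and no FPG criterion met.

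Report NOD incidence with and without the unconfirmed row, and state why HbA1c and FPG are handled differently.

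A count requiring two consecutive values may be added as a sensitivity analysis. On the base assumptions it gives no-effect rates of 0.6%, 1.5% and 2.8% with 2, 4 and 8 values. It should not replace the definition: it is stricter than the SAP's main criterion and would make HbA1c-based NOD impossible for anyone with one value.

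Cost: a few lines of SAP wording and one or two table rows, with no new data. The confirmed row will miss some true cases first seen at the last visit, but these stay visible in the unconfirmed row.
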